### 4.2 Secondary Objectives

At Days 85 and 169:

- assess disease activity using SLEDAI-2K, BILAG-2004 and PGA;
- evaluate the immunogenicity of RSLV-132 in subjects with SLE;
- assess improvement in tender or swollen joint count;
- assess improvement in patient reported outcomes using the FACIT-Fatigue scale;
- assess the proportion of subjects achieving a 50% improvement in CLASI activity score

At Day 169:

- assess the ability of subjects to reduce oral steroids at Day 169 relative to Day 85;
- evaluate the safety and tolerability of 22 weeks of RSLV-132 exposure;

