### 7.3 Concomitant Medications

Subjects entering the study who had no changes to their SLE medications in the previous 30 days prior to the Baseline visit shall remain on the background medications at the same doses throughout the study. With the exception of decreases in OCS, no changes in lupus medications shall be permitted during the study, including the addition of topical steroids or topical tacrolimus, except for the rescue of a lupus flare.

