### 7.4 Steroid Tapering

One of the objectives of the study is to evaluate the potential steroid sparing effects of RSLV-132. Steroid doses should remain stable through Day 85. Thereafter, Investigators shall decrease the use of oral corticosteroids beginning on Day 85 using the guidance below. No further steroid decreases should occur from Day 141 through Day 169.

- Subjects receiving  $>7.5$  mg of prednisone or equivalent daily AND demonstrating a clinical improvement in the cutaneous manifestations of lupus as measured by a decrease in the CLASI activity by 50% compared with Baseline shall decrease oral corticosteroids as follows:
  - Decrease prednisone (or equivalent) by 2.5 mg/day
  - If the prednisone dose (or equivalent) remains greater than 7.5 mg/day AND cutaneous disease activity remains improved (CLASI activity score decreased by 50% compared with baseline) AND prednisone has been stable for 2 weeks, reduce prednisone by an additional 2.5 mg; repeat after 2 more weeks.
  - If prednisone reduced to 7.5 mg, see below,
  - If after a decrease in prednisone, the CLASI is no longer decreased (compared to baseline) by 50%, the investigator may increase the prednisone to the previous daily dose (not to exceed the baseline dose)
- Subjects receiving  $\leq 7.5$  mg/of prednisone or equivalent daily AND demonstrating clinical improvement in the cutaneous manifestations of lupus as measured by a decrease

in the CLASI activity score by 50% compared with baseline, the investigator may, at his/her discretion, decrease prednisone by no greater than 2.5 mg/day every other week.

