### 11.3 Analysis of the Secondary Objectives

The following secondary objectives will be compared between the two treatment arms:

- The immunogenicity of RSLV-132 as measured by the presence of RSLV-132 antibodies
- Improvements (from Baseline to Day 85 and Day 169) in the SLEDAI-2K, PGA, and BILAG-2004 scores
- Improvement (from Baseline to Day 85 and Day 169) in the FACIT-Fatigue scale
- Improvements (from Baseline to Day 85 and Day 169) in tender or swollen joint count
- Reduction in oral steroids at Day 169 relative to Day 85
- The proportion of subjects achieving a 50% improvement in CLASI activity score

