9. EFFICACY ANALYSES

Efficacy analyses include assessing improvement in disease activity using CLASI, SLEDAI-2K, BILAG-2004, PGA, and FACIT-Fatigue scores; tender or swollen joint count; oral steroids use; as well as evaluating the autoantibody and complement profiles.

Each assessment will be summarized descriptively by treatment group on the FAS for all study visits at which the data were collected. No statistical testing will be performed, unless otherwise specified.

All data will be listed.

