9.2.6. Oral Steroids Tapering

One of the objectives of the study is to evaluate the steroid sparing effects of RSLV-132. The Investigators shall decrease the use of oral corticosteroids beginning on Day 85 using the guidance stated under SAP Section 2.3.4.1. No further steroid decreases should occur from Day 141 through Day 169. The reduction in oral steroids at Day 169 relative to Day 85 will be evaluated as part of the secondary efficacy endpoints.

Summary of observed values: (1) For those who were on any oral corticosteroids at Day 85, observed of corticosteroids dose values and the change from Day 85 at Day 169 will be summarized. (2) For those who were on any oral corticosteroids with >7.5 mg/day at Day 85, observed of corticosteroids dose values and the change from Day 85 at Day 169 will be summarized.

The summary of (1) or (2) will only be performed if there are 25% or more of the subjects in the RSLV-132 group were on any oral corticosteroids at Day 85 or were on any oral corticosteroids with >7.5 mg/day at Day 85 respectively. No statistical testing will be performed.

Dose equivalence to Prednisone:

Medication	Dose Equivalence to 10 mg	Dose Equivalence to 7.5 mg
Oral Prednisone	10 mg	7.5 mg
Cortisone	50 mg	37.5 mg
Hydrocortisone	40 mg	30 mg
Methylprednisolone	8 mg	6 mg
Prednisolone	10 mg	7.5 mg
Betamethasone	1.2 mg	0.9 mg
Dexamethasone	1.5 mg	1.125 mg
Budesonide	2.25 mg	1.6875 mg
Deflazacort	12 mg	9 mg

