12. SAP REVISION

Revision Date	Section	Summary of Revision	Reason for Revision
July 6, 2017	2.3.3	Updated Table 1 Study Procedures.	Protocol Amendment 4.0
	2.3.5	Updated that efforts will be made to perform all EOT and EOS assessments outlined in Protocol Appendix A.	Protocol Amendment 5.0
	6.2	Clarify the summaries.	Per sponsor request.
	6.3	Clarify to summarize the major protocol deviations.	Per sponsor request.
	7.1	Added the overall mean for prednisone or equivalent dose.	Per sponsor request.
	7.2	Clarify to summarize the Medical History Body Systems	Per sponsor request.
	9	Remove text “RSLV-132 plasma levels and RNase activity” from Efficacy Analyses.	They are not part of the efficacy analyses.
	9.2.2	No statistical testing will be performed for the imputed values of BILAG-2004 Index Assessment.	Per sponsor request.
	9.2.6	Specify to summarize at Day 169 only.	Per sponsor request.
	9.2.7	Remove text “Fisher’s exact test will be used for the treatment group comparison” under the summary of observed values.	No treatment group comparison will be made on observed values.
	9.3.1	Adding dsDNA as part of the autoantibody profile.	Protocol Amendment 4.0
		Adding a summary for the actual values.	Per sponsor request.
	10.1.2	Adding patient year calculations for the adverse event summary	Per sponsor request.

	10.2.1	Adding grade 3 or higher toxicity summaries for the safety lab data.	Per sponsor request.
	10.2.4	Replace text “Appendix B” with “Appendix A”.	Correct protocol reference.
		Physical exam results will be listed only.	Per sponsor request.
March 10, 2020	3.2.7	Revise baseline definition to consider screening.	Internal document consistency.
	6.2	Removing “plus 1” in the Total duration of infusion (Hours) calculation.	Clarification.
	9.1, 9.2.1, 9.2.3, 9.2.4 and 9.2.5	Adding repeated measurement analysis in addition to the LOCF imputation.	A less biased method by missing data compare to LOCF.
	9.1, 9.2.4, 9.2.7	Add non-censored summaries.	Per sponsor request.
	9.2.6	Include table of Predinsone Equivalent dosing.	Facilitate grouping of corticosteroids.
	10.2.4	Adding Physical Exam summary by categories of Normal/Abnormal (CS/NCS).	To be compliant with FDA ICH E3 guideline and to be consistent with Resolve RSLV-132-04 study.
	11	PK not in scope of SAP.	

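### SAP 9.2.6 produces the oral steroid summaries only if 25% of the RSLV-132 arm qualifies, so the between-arm summary of a secondary endpoint can go missing

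*SAP*

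**What the plan says.** Protocol 4.2 sets a secondary objective to "assess the ability of subjects to reduce oral steroids at Day 169 relative to Day 85". Protocol 11.3 puts "Reduction in oral steroids at Day 169 relative to Day 85" among the items to be compared between the two arms, and SAP 2.2.1.2 repeats it as a secondary efficacy endpoint on the treatment group difference.

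SAP 9.2.6 carries this out with two descriptive summaries and no test. Summary (1) is defined as follows: "For those who were on any oral corticosteroids at Day 85, observed of corticosteroids dose values and the change from Day 85" at Day 169. Summary (2) is the same for users above 7.5 mg/day at Day 85. Production is conditional: "The summary of (1) or (2) will only be performed if there are 25% or more of the subjects in the RSLV-132 group" meet the matching Day 85 criterion. The section sets no condition on placebo and names no substitute table.

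The opening of SAP 9 is more general: "Each assessment will be summarized descriptively by treatment group on the FAS for all study visits at which the data were collected". It also provides for listing all data.

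On steroid use before Day 85, Protocol 7.4 says "Steroid doses should remain stable through Day 85". Protocol 7.3 bars changes in lupus medication other than oral steroid decreases, "except for the rescue of a lupus flare". Protocol 7.5 lets the investigator treat a flare with steroids and then bring the subject back to the baseline dose.

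**The concern.** Steroid sparing is a declared objective. Whether the report contains any between-arm summary of it depends on a post-randomisation count in one arm only. If 8 of 33 RSLV-132 subjects and all 17 placebo subjects were users at Day 85, half the trial would be on steroids and summary (1) would still not be produced. No other efficacy endpoint in SAP 9 carries such a condition.

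A second, smaller matter is how the summary reads when it is produced. 9.2.6 takes the Day 85 dose as observed. A subject still on a rescue dose at that visit who later returns to baseline is recorded as having reduced steroids, and cannot be told apart from a subject who tapered. A flare alone can also bring a subject into the group above 7.5 mg/day and, in the RSLV-132 arm, into the 25% count.

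**Working it through.** **Inputs.** About 50 subjects (SAP 2.3.7), randomised 2:1 (SAP 2.3.6), so about 33 RSLV-132 and 17 placebo. The threshold is 25% of the RSLV-132 group (SAP 9.2.6). The share on oral steroids at Day 85, p, is not given in either document. I assume a range and take the same p in both arms. The plan has no figure of its own to reproduce, since the sample size was not based on power.

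**Count needed.** 0.25 × 33 = 8.25, so 9 RSLV-132 subjects must qualify; 8 or fewer drops the summary for both arms. For comparison, 25% of placebo is 0.25 × 17 = 4.25, so 5 subjects.

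**Probability that summary (1) is dropped.** P(X ≤ 8) with X ~ Bin(33, p). The chance that it is dropped although placebo reaches 25% is this value times P(Y ≥ 5) with Y ~ Bin(17, p).

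| Assumed p | P(dropped) | P(placebo ≥ 5) | P(dropped and placebo ≥ 5) |
|---|---|---|---|
| 20% | 0.800 | 0.242 | 0.193 |
| 25% | 0.553 | 0.426 | 0.236 |
| 30% | 0.304 | 0.611 | 0.186 |
| 40% | 0.044 | 0.874 | 0.039 |
| 50% | 0.002 | – | – |

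**Users left unsummarised when it is dropped.** E[X | X ≤ 8] + 17p:
- 20%: 5.76 + 3.40 = 9.2
- 25%: 6.45 + 4.25 = 10.7
- 30%: 6.89 + 5.10 = 12.0
- 40%: 7.38 + 6.80 = 14.2

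**Sensitivity to arm size, at p = 25%.** With 32 RSLV-132 subjects 8 are needed and P(dropped) = 0.43; with 33, 9 and 0.55; with 34, 9 and 0.51.

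**Denominator.** 9.2.6 does not say whether the 25% is taken over all treated RSLV-132 subjects or over those with Day 85 data. If 20% of the arm were lost by then (an assumption, leaving 26), the count needed would be 9 on the first reading and 0.25 × 26 = 6.5, so 7, on the second.

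**Summary (2).** Users above 7.5 mg/day are a subset of all users, so their share cannot be higher. At an assumed 10 or 15%, that table is dropped with probability 0.996 or 0.951. If only summary (2) fails its condition, summary (1) is still produced and contains the same subjects.

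**Rescue at Day 85 (assumed doses, to show the mechanism).** Baseline 10 mg, Day 85 20 mg for a flare, Day 169 10 mg: change from Day 85 = 10 − 20 = −10 mg; change from baseline = 10 − 10 = 0. One such subject among 9 moves the arm mean by −10/9 = −1.1 mg. The documents give no flare rate or flare dose, so no expected size follows.

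**The case against.** The condition is a disclosed, prespecified rule for producing a table in a study that disclaims formal hypothesis testing. When it fails, at most 8 of about 33 RSLV-132 subjects had a dose to reduce, and a mean change in so few says little about steroid sparing. Individual doses remain in the listings, SAP 7.1 tabulates baseline dose groups by arm without condition, and SAP 8.1 tabulates concomitant medication by arm. The probabilities rest wholly on assumed use rates, and from 40% use upward the risk nearly vanishes.

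Much of this stands. The loss is of a descriptive summary, not of data or of a test, and the use rates are assumptions. But neither the baseline table nor the medication table shows change in dose, and a listing is not a comparison of arms. Small numbers are a reason to print n beside the result rather than to withhold the table, and they do not explain why only one arm is counted.

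One could also argue that the general sentence in SAP 9 keeps the summary alive. That is possible, but 9.2.6 is the specific text and its condition is explicit. The SAP 12 entry "Specify to summarize at Day 169 only" concerns visit timing and does not settle which text prevails. At best the two sections disagree and need reconciling.

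On rescue, Protocol 7.4 expects stable doses to Day 85 and 7.5 calls for a quick return to baseline, so for most subjects Day 85 should equal baseline. The ambiguity is confined to those still above baseline at that visit.

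**Conclusion.** Followed as written, 9.2.6 can suppress the only planned between-arm summary of a protocol secondary endpoint. For the any-use summary the probability runs from 0.80 at 20% use to 0.002 at 50% use, with 33 RSLV-132 subjects and use rates that are assumptions throughout. The whole endpoint goes unsummarised only if summary (1) fails its condition. The harm is a missing descriptive summary. The plan should be changed because the remedy is nearly free.

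The rescue point is a real ambiguity in how the table would read, of unknown frequency and direction.

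A reader might infer more than the documents support:
- That the result would be biased towards RSLV-132. No flare rate, flare dose or user count is given, so no direction can be stated.
- That Day 85 is the wrong reference. It is the protocol's own reference, and stable dosing to that day makes it sound for most subjects.
- That leaving out subjects on 0 mg at Day 85 is an error. The endpoint is a reduction from Day 85, and such subjects have nothing to reduce; later starts lie outside it.
- That 9.2.6 contradicts the 60-day steroid censoring in SAP 9.1, 9.2.4 and 9.2.7. That rule belongs to additional summaries of other endpoints.

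**What to change.** Delete the 25% condition from SAP 9.2.6 so that summaries (1) and (2) are always produced for both arms with n shown. This also brings the section into line with Protocol 11.3 and the opening of SAP 9, and removes the denominator question. A threshold on the pooled sample would not do: 25% of 50 is 12.5, so 13 subjects, and the chance of loss would still be 0.81, 0.51, 0.22 or 0.01 at 20, 25, 30 or 40% use.

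Add to the same table, by arm, the number of included subjects whose Day 85 dose is above their baseline dose, so that return from rescue can be told apart from taper.

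Optionally, add a supportive descriptive table of Day 169 against Day 1 dose by arm on the full analysis set, with non-users as 0 mg. It would also show starts after Day 85, but it is an addition and not the cure for an error.

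The cost is a change of SAP wording and one added count from data already collected. The downside is a table that may have small counts. The endpoint, the Day 85 reference and all steroid rules stay as they are.

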9.2.7. CLASI Activity Score Improvement

CLASI Activity assessment will be performed for each subject at scheduled visits to determine the SLE disease activity for each subject at the visit. The assessment includes each anatomical location. Proportion of subjects achieving a 50% improvement (decrease) in CLASI total Activity score (defined as the sum of the scores from each anatomical location) will be evaluated as part of the secondary efficacy endpoints.

Summary of observed values: The number and percentage of subjects achieving a 50% improvement in CLASI Activity subsection score from baseline at each scheduled visit will be summarized. The percentages will be calculated based on the actual number of subjects at each visit in each treatment group of the FAS. No statistical testing will be performed.

Summary of imputed values: The number and percentage of subjects achieving a 50% improvement in CLASI Activity subsection score from baseline at each scheduled visit will also be analyzed on the imputed values. Fisher's exact test will be used for the treatment group comparison. LOCF will be used to impute missing values on the FAS.

Summary of non-censored values: Non-censored values and LOCF imputed non-censored values will be used to summarize the number and percentage of subjects achieving a 50% improvement in CLASI Activity subsection score from baseline at each scheduled visit. Fisher's exact test will be used for the treatment group comparisons. The following values will be censored based on blinded review before database lock:

- a. Values obtained within 60 days of a steroid (systemic/oral/topical but not ophthalmic or inhaled) dose that is increased above baseline for more than one day
- b. Addition of other systemic agents for lupus (such as antimalarials, methotrexate, rituximab, dapsone)

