5. GENERAL ANALYSIS METHODS

Continuous variables will be summarized using descriptive statistics including number of subjects (n), mean, standard deviation (SD), median, minimum, and maximum. Categorical variables will be summarized using frequencies and percentages. Percentages will be calculated using the total number of subjects in each treatment group for each applicable population and/or subpopulation, unless otherwise noted.

Number of subjects, minimums, and maximums will be calculated to the same number of decimal places as the source data. Means, standard deviations and quartiles will be calculated to one more decimal place than the source data. Percentages will be calculated to one decimal place. Zero count cells will be displayed as “0” with percentage of (0%). Unless otherwise noted, summaries will be performed by the treatment group (Placebo and RSLV-132 10 mg/kg).

If statistical tests are performed, the tests will be done at the two-sided, 5% significance level to compare Placebo vs. RSLV-132 10 mg/kg, unless otherwise specified. The point estimate and 95% confidence interval (CI) for the treatment differences may be displayed along with the p-value for the treatment comparison. P-values will be presented to three decimal places. P-values < 0.0005 will be presented as < 0.001. P-values greater than 0.999 will be presented as > 0.999.

In the absence of any predefined hypotheses in this study, the general strategy of the analysis will be to examine the data summaries for any trends amongst the treatment groups. No formal hypothesis testing will be carried out. P-values obtained from statistical testing of the analyses will be used for descriptive purposes only.

All data collected in the clinical database will be included in the data listings, as appropriate. Subjects who were randomized and never treated will be accounted for in the data listings.

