9.1. Analysis of Primary Efficacy Endpoints

The primary efficacy endpoints are the improvements from Baseline (Day 1) to Day 85 and Baseline to Day 169 CLASI Activity scores.

CLASI Activity assessment will be performed for each subject at scheduled visits to determine the SLE disease activity for each subject at the visit. The assessment includes each anatomical location. The total score of the Activity subsection (defined as the sum of the scores from each anatomical location) will be used in the summary. The improvements from Baseline (Day 1) to Day 85 and from Baseline (Day 1) to Day 169 in the total activity score will be evaluated as part of the primary efficacy endpoints. Lower score represents less disease activity.

Summary of observed values: Observed values of total Activity score and the change and percent change from baseline at each scheduled visit will be summarized. In addition to the LOCF imputation described below, the primary endpoints (change from Baseline on observed values) will be analyzed using Mixed effect Model Repeat Measurement (MMRM) method. The MMRM model will include the fixed categorical effects of treatment, random effect visit, and treatment-by-visit interaction, as well as continuous fixed covariates of baseline score and baseline score-by-visit interaction. An unstructured covariance structure of random effect will be used for modeling the within-subject errors.

Summary of imputed values: LOCF imputed values and the change and percent change from Baseline (Day 1) in the CLASI Activity total score at Days 85 and 169 and at each scheduled visit will also be analyzed. The two-sample t-test will be used for the treatment group comparison on the change from Baseline.

Summary of non-censored values: Non-censored values and LOCF imputed non-censored values as well as the change and percent change from Baseline (Day 1) in the CLASI Activity total score at Days 85 and 169 and at each scheduled visit will also be analyzed. The two-sample t-test will be used for the treatment group comparison on the change from Baseline. The following values will be censored based on blinded review before database lock:

- a. Values obtained within 60 days of a steroid (systemic/oral/topical but not ophthalmic or inhaled) dose that is increased above baseline for more than one day
- b. Addition of other systemic agents for lupus (such as antimalarials, methotrexate, rituximab, dapsone)

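### SAP 9.2.7: both LOCF-based CLASI-50 comparisons can count withdrawn or rescued subjects as responders, and the version that could avoid this states no denominator

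*SAP*

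**What the plan says.** SAP 9.2.7 describes four versions of CLASI-50.

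- **Observed values.** "The percentages will be calculated based on the actual number of subjects at each visit in each treatment group of the FAS". No test.
- **LOCF values.** "LOCF will be used to impute missing values on the FAS". Fisher's exact test. No censoring is applied.
- **Non-censored values, without and with LOCF.** "Non-censored values and LOCF imputed non-censored values will be used to summarize the number and percentage of subjects achieving a 50% improvement". For these, Fisher's "exact test will be used for the treatment group comparisons"; the plural covers both. No denominator is given.

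Censoring is introduced by "The following values will be censored based on blinded review before database lock". Rule a covers values within 60 days of a steroid "dose that is increased above baseline for more than one day" (the same words stand in 9.1 and 9.2.7). Rule b reads "Addition of other systemic agents for lupus (such as antimalarials, methotrexate, rituximab, dapsone".

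Elsewhere, SAP 3.2.5 makes LOCF the general rule for missing efficacy values. SAP 5 sets the default denominator for percentages, "using the total number of subjects in each treatment group for each applicable population and/or subpopulation, unless otherwise noted". SAP 3.1.2 keeps in the FAS every randomized subject who had one dose. SAP 2.3.4.2 lets a subject with a flare be treated and remain in the study, and SAP 2.3.5 allows withdrawal with no further data. Neither document says that a rescued or withdrawn subject counts as a CLASI-50 non-responder.

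**The concern.** A response rate at Day 169 is naturally read as the share of treated subjects who were better at that visit on study treatment and background therapy. LOCF answers a different question: whether the last available score met the criterion. For a subject who left, or whose later scores are set aside because of rescue, that score may be weeks old and may precede the deterioration that led to rescue. In plain LOCF it may also be a score obtained on the rescue drug.

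The SAP's revision log (section 12) shows that the non-censored summaries were added in March 2020. They set rescue-affected scores aside, but carrying the pre-rescue score forward can return the same subject to the responder column. The study is a proof of concept intended to precede a larger phase 2 trial (Protocol 4). With about 50 subjects, a few such classifications change how the rate reads.

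**Working it through.** There is no stated response, rescue or withdrawal rate and no power calculation (SAP 2.3.7), so there is no figure of the plan's own to reproduce. The check has three parts.

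**1. How each version treats a withdrawn or rescued subject**

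| Version | Withdrew, last score met the criterion | Rescued, visit value censored under rule a or b | Fisher test |
|---|---|---|---|
| Observed | leaves the denominator | scored on the visit value | no |
| LOCF | responder | scored on the visit value, on rescue | yes |
| LOCF non-censored | responder, if that score is not censored | scored on the last non-censored value | yes |
| Non-censored, unimputed | non-responder or excluded: not stated | non-responder or excluded: not stated | yes |

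**2. What the 60 days do to Day 169**

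Post-baseline CLASI visits are Days 29, 57, 85, 99, 113, 127, 141, 155 and 169 (Protocol Appendix A). Take a steroid increase on Day 120.

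- Window running forward from the increase: the gaps to Days 127, 141, 155 and 169 are 7, 21, 35 and 49 days. All are at most 60, so all four are censored. Day 113 is the last kept value and decides Day 169. The subject is a responder if Day 113 was at least 50% below baseline.
- Window running both ways: 120 − 60 = 60, so Days 85, 99 and 113 are censored too, and Day 57 decides Day 169.

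The wording of rule a does not choose between these readings. Nor does it say whether the count starts at the first or the last raised dose. On the forward reading the nominal cut-off is 169 − 60 = Day 109. Protocol 12.1 allows ±5 days at Day 169, so it lies between 164 − 60 = Day 104 and 174 − 60 = Day 114, depending on the actual visit date. Rule b names an event without saying which values it removes or for how long.

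**3. What one subject is worth**

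Assume 50 subjects at 2:1, that is 33 and 17. One subject is 1/33 = 3.0 points (RSLV-132) or 1/17 = 5.9 points (placebo). The counts below are assumptions, and the base case was chosen close to p = 0.05. P-values are two-sided Fisher.

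| Case | RSLV-132 | Placebo | Difference (points) | p |
|---|---|---|---|---|
| Base | 15/33 | 2/17 | 33.7 | 0.026 |
| Two RSLV-132 and one placebo subject added as responders | 17/33 | 3/17 | 33.9 | 0.032 |
| Two placebo subjects added | 15/33 | 4/17 | 21.9 | 0.218 |
| Two RSLV-132 subjects added | 17/33 | 2/17 | 39.8 | 0.007 |

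For the unstated denominator, assume 15 and 3 responders and that 6 of 33 and 3 of 17 subjects (about 18% per arm) have no usable value:

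- all FAS subjects: 15/33 v 3/17 = 45.5% v 17.6%, 27.8 points, p = 0.067;
- subjects with a value: 15/27 v 3/14 = 55.6% v 21.4%, 34.1 points, p = 0.051.

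The choice of denominator alone moves the difference by 6.3 points.

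**The case against.** The best defence is that the analysis wanted is nearly there. The numerator of the unimputed non-censored version holds only subjects with their own uncensored value at the visit. SAP 5 makes the group total the default denominator unless noted otherwise, SAP 9 places efficacy summaries on the FAS, and only the observed-values paragraph of 9.2.7 notes otherwise. On that reading, censored and missing subjects already act as non-responders, with a Fisher test. This largely stands. It stops short of settling the matter because the same default sentence also allows a subpopulation, which could mean subjects with a value.

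A reader might infer that the planned tables cannot separate subjects counted on an older score. The documents do not support that: both non-censored versions are reported at each visit, so the LOCF numerator minus the unimputed one gives that count, and the data are listed.

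Nor does LOCF always create responders. SAP 2.3.5 calls for efforts to obtain end-of-treatment assessments after early discontinuation; if that score feeds LOCF, a lost response is picked up. On the forward reading from onset, a steroid increase on Days 25 to 29 removes Days 29, 57 and 85, so Day 85 could rest only on baseline, which is non-response.

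It is also fair that neither document defines rescue or withdrawal as treatment failure, and that blinded review protects against censoring choices that depend on arm. That review, however, does not settle which value is carried or the denominator.

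**Conclusion.** The point holds as a minor one. Both LOCF versions of CLASI-50, each with a Fisher comparison, can count withdrawn or rescued subjects as responders. The version closest to a non-responder analysis depends on a denominator that 9.2.7 leaves open.

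A reader might go further and infer that the plan favours RSLV-132. The documents do not support that: they give no rates, and the effect depends on which arm has more withdrawals and rescue. In the balanced illustration the difference hardly moves (33.7 to 33.9 points). The shift of 3.0 or 5.9 points per subject rests on the assumed 33:17 split, and the p-values rest on assumed counts. CLASI-50 is secondary, and SAP 2.3.7, 3.2.3 and 5 exclude formal testing, so what is at stake is how the rate is read, not an error rate.

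**What to change.** In SAP 9.2.7:

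1. State that the non-censored CLASI-50 summary at Days 85 and 169 has all FAS subjects of the group in the denominator. Count as non-response any visit value that is censored under rule a or b, or is missing after withdrawal. A subject who stops study drug but continues assessments is scored on the actual value unless it is censored.
2. Keep the LOCF versions as sensitivity analyses.
3. State the direction and starting point of the 60 days in rule a, applied to actual visit dates, and the period of values that rule b removes. The same rules appear in 9.1 and 9.2.4 and should be kept identical there.
4. Describe the result as response at the visit without recent rescue. A subject rescued early enough for the visit value to be uncensored is still scored on that value, so the analysis does not show response free of rescue throughout. Counting rescue at any earlier time as non-response can be a further sensitivity analysis.

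The cost is SAP wording and programming, with no new data. Response rates will be somewhat lower in both arms, and some withdrawals or steroid increases unrelated to lupus will count as non-response.
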